# **Assessment of Er:YAG (yttrium-aluminium-garnet) Laser-Assisted Surgical Treatment in Medication-Related Osteonecrosis of the Jaw (MRONJ): A Clinical Trial**

## Study Protocol

1. Examination and qualification of patients
2. Taking X-ray and performing CBCT.
3. Initiation of antibiotic therapy: amoxicillin with clavulanic acid (875 mg + 125 mg) every 12 hours. In patients allergic to penicillin, clindamycin (600 mg every 12 hours). The antibiotic must be taken 3 days before the procedure and continued 14 days after the treatment.
4. Scheduling follow-up visits 1 and 2 weeks post-procedure and at 3 and 6 months. Assessment of the condition of the surrounding mucosa, wound healing, complications and overall treatment effectiveness.
5. Anesthesia of patients using anesthesia without vasoconstrictor additives (Mepivacaine 3%, Scandodenst, Septodont). Creating access with a 15C scalpel and detaching tissues using a raspator with a semicircular tip (15 mm in diameter).

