### Procedure:

- a. Study group: Tissue debriding until hard, healthy, lively bleeding bone is exposed using Er:YAG laser with parameters: 400mJ, 6W, 15Hz, 5/8 water cooling, laser tip with a diameter of 800 microns.
- b. Control group: Tissue debriding until hard, healthy, lively bleeding bone is exposed using rose-shaped rotary drills (8 mm diameter) with water cooling at a speed not exceeding 40.000 rpm.

Closing wounds with 5/0 non-resorbable sutures and taking them off after 2 weeks.

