## Statistical analysis

1. Characterizing the study sample in terms of variables included in the study.
2. Highlighting treatment effectiveness indicators.
3. Performing logistic regression analysis.
4. Using the Student's t-test for intergroup differences.

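### The plan does not say who scores the outcomes, by what criteria, or whether the scorer is masked, and it leaves the effectiveness indicators open until results by arm could be known

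*Combined protocol and SAP*

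**What the plan says.** The follow-up schedule is in Study Protocol, item 4: "Scheduling follow-up visits 1 and 2 weeks post-procedure and at 3 and 6 months". The same item names what is assessed: "Assessment of the condition of the surrounding mucosa, wound healing, complications and overall treatment effectiveness". That is four domains at four time points. None has a criterion, scale or threshold, and no domain or visit is designated primary. Imaging appears once, in item 2 ("Taking X-ray and performing CBCT"), among the steps before the procedure. No follow-up imaging and no imaging-based outcome is stated.

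Under Procedure, the arms differ by instrument. One reads "Study group: Tissue debriding until hard, healthy, lively bleeding bone is exposed using Er:YAG laser with parameters" and the other "Control group: Tissue debriding until hard, healthy, lively bleeding bone is exposed using rose-shaped rotary drills". Closure is written once for both: "Closing wounds with 5/0 non-resorbable sutures and taking them off after 2 weeks".

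The Statistical analysis section has "Highlighting treatment effectiveness indicators" as its item 2, followed by logistic regression and Student's t-test. No outcome is named for either method. The documents do not mention masking of patients, assessors or analysts, do not identify the scorer, and do not describe the study team.

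**The concern.** Mucosal condition, wound healing and overall effectiveness call for a clinician's judgement, and complications have no written definition either. With no criteria, much is left to the scorer's discretion. The operator knows which instrument was used, and nothing in the plan prevents the operator from scoring his or her own cases. A scorer who expects the laser to do better may read doubtful cases in its favour.

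A second route to bias comes later. Because the effectiveness indicators are plural and undefined, the plan permits choosing among domains and visits once results by arm are known.

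Neither the t-test nor the logistic regression can correct scores that were biased when recorded. A significant difference in favour of the laser could then not be separated from scorer expectation or from selective choice of indicator.

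**Working it through.** The plan states no sample size, significance level, success rate or power, so there is no figure of its own to reproduce. The calculation below is an illustration of misrating only. It does not measure the effect of choosing indicators late.

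**Assumed inputs (none from the documents).** No true difference between arms; true healing p = 0.70 or 0.80 in both; equal arms of n = 20, 30 or 50; healing scored 0/1; two-sided 5% level. The scorer upgrades a fraction u of unhealed laser cases and downgrades a fraction d of healed drill cases. The test is the pooled two-sample t-test. The plan names the t-test but not its outcome, so using it on 0/1 healing is also an assumption.

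**Formulas.**
- Apparent laser rate = p + (1 − p)u
- Apparent drill rate = p(1 − d)
- False-positive rate = sum, over all pairs of arm totals, of the binomial probability of each pair for which |t| exceeds the 97.5% point of t on 2n − 2 degrees of freedom

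**Worked case.** p = 0.80, u = 0.25, d = 0.05: laser 0.80 + 0.20 × 0.25 = 0.85; drill 0.80 × 0.95 = 0.76; spurious difference 9 points.

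**Results (exact enumeration).**

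| p | u | d | Apparent laser v drill | False positives at n = 20 / 30 / 50 |
|---|---|---|---|---|
| 0.80 | 0 | 0 | 80.0% v 80.0% | 5.0 / 4.9 / 4.9% |
| 0.80 | 0.10 | 0.02 | 82.0% v 78.4% | 5.9 / 6.2 / 7.2% |
| 0.80 | 0.25 | 0 | 85.0% v 80.0% | 6.9 / 7.9 / 9.7% |
| 0.80 | 0.25 | 0.05 | 85.0% v 76.0% | 10.8 / 13.8 / 20.2% |
| 0.80 | 0.50 | 0.10 | 90.0% v 72.0% | 30.7 / 43.2 / 64.3% |
| 0.70 | 0 | 0 | 70.0% v 70.0% | 5.3 / 4.9 / 5.0% |
| 0.70 | 0.10 | 0.02 | 73.0% v 68.6% | 6.4 / 6.5 / 7.7% |
| 0.70 | 0.25 | 0 | 77.5% v 70.0% | 8.6 / 9.9 / 13.7% |
| 0.70 | 0.25 | 0.05 | 77.5% v 66.5% | 12.4 / 15.5 / 23.2% |
| 0.70 | 0.50 | 0.10 | 85.0% v 63.0% | 36.4 / 50.0 / 72.5% |

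Without misrating the test holds its level, so the excess in the other rows comes from misrating alone. In the worked case at n = 50, 20.1 of the 20.2 points favour the laser.

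**Second model.** A pooled two-proportion z-test, with upgrading of laser failures only, gives a spurious difference of u(1 − p). At p = 0.70 and u = 0.30 this is 0.30 × 0.30 = 9 points, and false positives are 9.9%, 12.4% and 17.7% at 20, 30 and 50 per arm. If only a quarter of assessments were unmasked, the difference would be 0.25 × 9 = 2.25 points and false positives 5.3%, 5.4% and 5.7%. Masking therefore helps in proportion to how complete it is. The documents give no basis for saying how complete it would be.

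**The case against.** The strongest reply is that the documents are silent rather than wrong. They do not say that the operator scores. Closure is the same in both arms and no arm-specific sign at follow-up is described, so a clinician who was not at surgery could well be unaware of the arm. This stands. A reader might infer that outcomes are scored with the arm visible, but only the operator's knowledge follows from the text.

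A reader might also infer that the outcome is a single global judgement. It is not: overall effectiveness is one of four listed domains, the other three are more specific, and complications may include discrete events. What remains is that none of the four is defined and none is primary.

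The illustration can also be pressed. Its larger figures need misrating in both directions at once, and mild misrating leaves the error rate close to 5%. That is fair, and it is why the low scenarios are in the table.

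Finally, it would be tempting to claim that the existing team could remove most of the bias. Staffing is not described and the size of the bias is unknown, so that claim has no support. In particular, a form carrying only a study number does not mask a surgeon who remembers the patient.

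**Conclusion.** The concern holds as an unaddressed risk of biased assessment and of selective choice of indicator, not as a demonstrated bias. As written, the plan allows operator-scored outcomes without criteria and a choice of indicator made after results by arm are seen.

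Against a nominal 5%, with no true difference and 20 to 50 per arm, the assumed scenarios give these false-positive rates:
- **Mild misrating (10% up, 2% down):** about 6-8% over 70-80% healing.
- **Upgrading only (25% up, none down):** about 7-10% at 80% healing and 9-14% at 70%.
- **Moderate (25% up, 5% down):** about 11-23% over 70-80% healing.
- **Heavy (50% up, 10% down):** about 31-64% at 80% healing and 36-73% at 70%.

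All of this rests on assumed sample sizes, healing rates, misrating rates and a 0/1 outcome. The plan should be changed because bias in recorded scores cannot be taken out afterwards.

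**What to change.** Amend Study Protocol item 4 and Statistical analysis item 2, using the visits and staff already in place.

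1. **Define the outcome.** Before any outcome data are seen by arm, name one effectiveness indicator with fixed yes/no criteria at one named visit. An example, for the investigators to agree or replace, is complete mucosal cover with no exposed or probeable bone, no fistula and no infection at 6 months. The documents themselves do not single out that visit.
2. **Separate scoring from operating where possible.** If the team already has a clinician who did not operate on the patient, that clinician scores the indicator without access to the operative record.
3. **Hold the arm list apart.** Keep it in a separate file and merge it only after the scores and the indicator are locked.

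If one clinician both operates and scores, apply steps 1 and 3 and report the outcome as unmasked. Those steps limit scoring discretion and selective choice of indicator, but they do not mask the scorer.

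The cost is protocol wording, a revised visit form and some reassignment of who completes it. No visit, procedure or person is added. The limitation is that masking stays incomplete in a single-clinician team.

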### Procedure:

- a. Study group: Tissue debriding until hard, healthy, lively bleeding bone is exposed using Er:YAG laser with parameters: 400mJ, 6W, 15Hz, 5/8 water cooling, laser tip with a diameter of 800 microns.
- b. Control group: Tissue debriding until hard, healthy, lively bleeding bone is exposed using rose-shaped rotary drills (8 mm diameter) with water cooling at a speed not exceeding 40.000 rpm.

Closing wounds with 5/0 non-resorbable sutures and taking them off after 2 weeks.

## Statistical analysis

1. Characterizing the study sample in terms of variables included in the study.
2. Highlighting treatment effectiveness indicators.
3. Performing logistic regression analysis.
4. Using the Student's t-test for intergroup differences.

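### Must item 3 of the statistical plan fix Firth penalised likelihood before the logistic regression is run?

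*Combined protocol and SAP*

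**What the plan says.** The Statistical analysis section has four one-line items. Item 3 is "Performing logistic regression analysis" and nothing more. Item 4, "Using the Student's t-test for intergroup differences", gives the comparison of the two groups to a different method. Item 2, "Highlighting treatment effectiveness indicators", names no endpoint. The possible outcomes have to be inferred from item 4 of the Study Protocol, which lists "Assessment of the condition of the surrounding mucosa, wound healing, complications and overall treatment effectiveness" without definitions or expected frequencies, over four visits: "Scheduling follow-up visits 1 and 2 weeks post-procedure and at 3 and 6 months". No sample size, significance level, event rate or covariate list appears anywhere, and the plan does not say whether treatment arm enters the regression.

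**The concern.** Logistic regression needs a categorical outcome, normally yes/no. Complications or failure to heal could be infrequent and the arms could be small. If an arm, or a level of another factor, then has no events or only events, the maximum-likelihood log odds ratio runs off to infinity. The Wald p-value and interval become products of the software's stopping rule. For 0/20 versus 4/20 the reported log odds ratio was -10.2, -14.6 or -22.2, with p = 0.82, 0.98 or 0.999, depending on routine and iteration limit.

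Likelihood-ratio, penalised and exact methods still work in that situation, but they can disagree near 5%. An analyst who chose among them after seeing the table could choose the verdict. The proposed remedy was to fix Firth penalised likelihood with profile intervals in advance.

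**Working it through.** The plan has no figure to reproduce. Every size and rate below is an assumption, with two equal arms, arm as the only term and a two-sided 5% level.

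**One sparse table, 0/20 versus 4/20 failures**

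- Likelihood ratio: the fitted log-likelihood is 4 ln 0.2 + 16 ln 0.8 = -10.008. With a common rate of 4/40 = 0.1 it is 4 ln 0.1 + 36 ln 0.9 = -13.003. Twice the difference is 5.99, so p = 0.014.
- Score test (Pearson chi-square): z = 0.20 / √(0.1 × 0.9 × 2/20) = 2.11, so p = 0.035.
- Firth: half an event and half a non-event are added to each arm. The odds ratio is (0.5/20.5)/(4.5/16.5) = 0.089. Twice the drop in penalised log-likelihood is 2 × (15.331 - 13.274) = 4.11, so p = 0.043 (profile interval 0.001 to 0.933).
- Fisher: 2 × C(20,4)/C(40,4) = 2 × 4,845/91,390 = 0.106.
- Student's t-test on the 0/1 data, as item 4 might be read: p = 0.036.

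The sensitivity to method is real for this table.

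**How often an arm is empty**

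With a and b the chances of no failure in each arm, (1 - rate)^n, exactly one arm is empty with probability a + b - 2ab. For 5% versus 20% and 20 per arm, a = 0.95^20 = 0.358 and b = 0.80^20 = 0.0115, which gives 0.36. At 15, 30, 50 and 100 per arm the figure is 47%, 22%, 8% and 0.6%. For 15% in both arms and 30 per arm it is 1.5%.

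**Rejection rates over all possible tables** (Wald counted as not significant when a cell is empty)

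| Assumed scenario | Wald | Likelihood ratio | Firth | Fisher |
|---|---|---|---|---|
| 20 per arm, 5% vs 20% | 3.9% | 36.6% | 29.2% | 16.8% |
| 20 per arm, 10% vs 10% | 0.2% | 8.5% | 3.9% | 1.2% |
| 20 per arm, 30% vs 60% | 44.6% | 46.3% | 44.7% | 34.7% |
| 100 per arm, 5% vs 20% | 90.2% | 92.1% | 91.7% | 88.3% |

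**Where the disagreement comes from**

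In the first row the four methods fail to agree in 33.1% of trials. The gap between likelihood-ratio and Wald accounts for 36.6 - 3.9 = 32.7 points of that. Between likelihood-ratio and Firth the gap is 36.6 - 29.2 = 7.4 points. At 50 and 100 per arm those two methods disagree in 2.9% and 0.4% of trials. Fisher sits 29.2 - 16.8 = 12.4 points below Firth because it is conservative.

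In the third row Wald and Firth differ by 0.1 point, and Wald, likelihood-ratio and Firth fail to agree in 1.7% of trials.

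**Whether Firth is needed**

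The score test needs no finite odds ratio. At 20 per arm it rejects in 29.2% of trials (5% versus 20%) and 3.9% (10% in both arms), the same as Firth. At 30 per arm its power is 45.3% against 39.2% for Firth, with type I error 5.4% against 4.1%.

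**The case for a change.** The best argument for acting is that the change costs one sentence and removes a choice that could decide the result. Default Wald output has almost no power in the sparse scenario. The likelihood-ratio test overshoots its nominal level (8.5%), and Fisher gives up power. An empty cell is not even required: at 1/20 versus 6/20, Wald gives 0.065, likelihood-ratio 0.030, Firth 0.043 and Fisher 0.091. Inference type matters within Firth as well, since its Wald version gives 0.114 and 0.069 on the two example tables and so reverses the profile-likelihood verdict. When events are plentiful Firth changes almost nothing (odds ratio 0.429 becomes 0.433 at 30/100 versus 50/100).

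All of these figures stand, and a method named in advance is better than one chosen afterwards. They do not establish that sparsity will arise, because the plan gives no size or rate from which to judge. Nor do they single out Firth, since score and exact tests are also defensible.

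The proposed sentence also reaches past the fitting method:

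- By adding per-arm risks and a Fisher test and naming one p-value to interpret, it presumes that arm is in item 3, although item 4 sends group differences to the t-test. If item 3 is a prognostic model without arm, those additions check nothing in it.
- Its fallback covers no events in either arm but not events in every patient, which is what universal success would be if the outcome were coded as healing.
- It does not limit the model to one record per patient, although there are four visits.

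**Conclusion.** No change to the plan follows from this point. Item 3 leaves its inference method unwritten, and that is missing detail which an analyst can fill sensibly. Separation shows itself in the output through an enormous standard error and a p-value near 1, and standard methods that survive it are available. Asking for Firth specifically is a preference.

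The size depends wholly on assumed figures. Among methods that work under separation, likelihood-ratio and Firth disagree in 7.4% of trials at 20 per arm with 5% versus 20% failures, and in 0.4% at 100 per arm; Fisher stands further apart because it is conservative. With a common outcome the choice among Wald, likelihood-ratio and Firth hardly matters. A residual freedom remains near the 5% line if the outcome proves rare and the arms small, and neither can be shown from the documents. The undefined outcome, visit, regressors and division of work between items 3 and 4 come before any question of fitting method. They form a separate matter, which naming Firth would not settle.

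### Item 4 names Student's t-test: if group sizes and spreads both differ, the pooled form can err in either direction, and Welch's form avoids this at almost no cost

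*Combined protocol and SAP*

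**What the plan says.** The statistical analysis section has four one-line items. Item 4 is "Using the Student's t-test for intergroup differences". It does not say whether variances are pooled, which outcome or visit is tested, or what happens if the spreads differ. Item 3 is "Performing logistic regression analysis", with neither outcome nor covariates named. Item 1 is descriptive: "Characterizing the study sample in terms of variables included in the study".

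There are two groups, laser and rotary drill. The second is introduced as "Control group: Tissue debriding until hard, healthy, lively bleeding bone is exposed using rose-shaped rotary drills". On how patients enter the trial, the study protocol section says only "Examination and qualification of patients". No sample size, allocation ratio, randomisation or matching appears in any section.

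The outcomes are given as broad domains: "Assessment of the condition of the surrounding mucosa, wound healing, complications and overall treatment effectiveness". None has a defined scale, and none is declared continuous. The visit schedule is "Scheduling follow-up visits 1 and 2 weeks post-procedure and at 3 and 6 months", but no visit is singled out for analysis.

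**The concern.** In ordinary usage, Student's t-test for two independent groups is the version that pools the two sample variances; the unequal-variance version is called Welch's test. An analyst who follows item 4 literally would pool.

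Pooling keeps the nominal error rate if the true variances are equal or the groups are about the same size. The plan secures neither. If both conditions fail, the pooled standard error is wrong, and the direction depends on which group is more variable. If it is the smaller group, the standard error is too small and false positives rise. If it is the larger group, the standard error is too large, so the test becomes conservative and any interval built on it is too wide. A reader of the plan could not tell which case applies.

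Unequal spread is plausible if healing is scored on a bounded scale, because the better-healing group may bunch near the top. The documents do not establish that such a scale will be used.

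**Working it through.** The plan states no sample size, SD, alpha or effect, so there is no figure of its own to reproduce.

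**Inputs.** From the documents: two groups and Student's t-test. Assumed: two-sided 5%, normal data, group sizes from 15:15 to 30:30 (equal) and from 12:18 to 10:30 (unequal), and SD ratios from 1 to 2 in either direction.

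**Formulas.** The pooled test uses, on average,

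SE_pooled² = [((n1−1)s1² + (n2−1)s2²)/(n1+n2−2)] × (1/n1 + 1/n2),

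while the true value is SE_true² = s1²/n1 + s2²/n2. The large-sample rejection rate under the null is 2 × [1 − Φ(1.96 × SE_pooled/SE_true)].

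**15 v 30, SD 2 in the smaller group, 1 in the larger.**
- SE_pooled² = [(14×4 + 29×1)/43] × (1/15 + 1/30) = (85/43) × 0.1 = 0.1977
- SE_true² = 4/15 + 1/30 = 0.3000
- SE ratio = √(0.1977/0.3000) = 0.812; rejection rate = 2 × [1 − Φ(1.591)] ≈ 11.2%

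**15 v 30, SD 1 in the smaller group, 2 in the larger.**
- SE_pooled² = [(14×1 + 29×4)/43] × 0.1 = (130/43) × 0.1 = 0.3023
- SE_true² = 1/15 + 4/30 = 0.2000
- SE ratio = √(0.3023/0.2000) = 1.229; rejection rate = 2 × [1 − Φ(2.410)] ≈ 1.6%

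**Equal sizes.** With n1 = n2 = n, SE_pooled² = [(s1² + s2²)/2] × (2/n) = (s1² + s2²)/n = SE_true². The bias vanishes whatever the SD ratio. Likewise, with s1 = s2 the two expressions agree whatever the sizes.

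**Simulation, pooled test, no true difference** (100,000 trials per setting for 15:30; 200,000 for the others):

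| Sizes | SD ratio | Larger SD in smaller group | Larger SD in larger group |
|---|---|---|---|
| 12:18 | 1.5 | 7.03% | 3.59% |
| 12:18 | 2 | 8.60% | 3.08% |
| 20:30 | 2 | 8.44% | 2.87% |
| 15:30 | 1.5 | 8.5% | 2.7% |
| 15:30 | 2 | 11.3% | 1.7% |
| 20:40 | 2 | 11.22% | 1.79% |
| 10:30 | 2 | 15.53% | 0.91% |

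A repeat of the 15:30, ratio 2 setting gave 11.1% and 1.7%. With equal sizes (15:15, 20:20, 30:30) and SD ratios up to 2, the pooled test rejected 4.96–5.31%. With unequal sizes and equal SDs it rejected 4.95–5.07%. Welch's test stayed between 4.9% and 5.2% in every setting.

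**Interval coverage.** At 10:30 with SD ratio 2, a nominal 95% pooled interval covers 84.5% or 99.1%, depending on direction. On a simulated bounded 0–10 score with a real difference between groups, pooled coverage was 88.3% or 98.3%, against about 95% for Welch. That is one illustrative configuration.

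**Cost of Welch when SDs are equal** (effect 0.9 SD, Student v Welch power): 79.1% v 79.1% at 20:20; 79.4% v 78.4% at 15:30.

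**The case against.** The strongest reply is that this is a secondary detail of a line that leaves out more important things. The variance form is not written down, so pooling is inferred from the name. No continuous or scored outcome is defined, and the planned logistic regression suggests that at least one outcome is categorical. The t-test may therefore reach no efficacy outcome at all, and the logistic regression could itself supply the group comparison. All of this stands, and it lowers the priority.

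A second reply is that bunching at the top of a scale occurs because one group does better, whereas the headline rejection rates assume no difference. This stands in part. Unequal spread with equal means needs another cause, such as groups that were not comparable at the start; no stated randomisation or matching rules that out, but nothing shows it either. Where a real difference causes the unequal spread, interval coverage is what suffers, and the bounded-score check shows that this can happen and that Welch largely corrects it.

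A reader might infer more: that the plan mandates pooling, that either unequal sizes or unequal spreads alone invalidate the test, or that the groups will in fact be unequal. The documents support none of these. They are silent on variance form and on group size, and the calculations show that a material error needs both inequalities together. The plan also promises no confidence interval, so poor coverage is a fault only of an interval that someone might add.

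**Conclusion.** The point holds as a cheap, conditional improvement. Item 4 names a test that is ordinarily the pooled form, and nothing in the documents keeps group sizes equal. If sizes and spreads both differ, the test of a continuous or scored outcome can be too liberal or too conservative: about 11% or 1.7% at a nominal 5% for 15 v 30 and an SD ratio of 2. If either is equal, the error is negligible (about 5.0–5.3%).

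The size rests wholly on assumed group sizes, SD ratios, alpha and normal data, none of which the documents supply. It would be wrong to read 11% as this trial's error rate. The priority is below that of defining the outcomes, their scales, the analysis visit, alpha and the sample size, but settling those would not by itself settle the variance form.

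**What to change.** Change item 4 to: 'For continuous or scored outcomes, Welch's unequal-variance t-test, with the mean difference and its Welch 95% confidence interval.' Name the outcome and visit to which it applies. Use it unconditionally, without a preliminary test of equal variances, so that the choice of test does not depend on the data. No matching change is needed for the logistic regression in item 3, which has no residual variance parameter.

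The cost is one phrase in the plan and one software option. In the equal-variance cases computed, the loss is about 1 percentage point of power or less: none at 20:20, and 79.4 − 78.4 = 1.0 point at 15:30.
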